### Gender of Subjects.

The study will include male subjects and non-pregnant female subjects.

### Age of Subjects.

Adults (age  $\geq$  18 years old) will be included. Exparel® is currently only approved in patients  $\geq$  18 years old.

### Racial and Ethnic Origin.

Subjects of all racial and ethnic origins will be included in the study.

**Inclusion Criteria.**

We will include adult patients ( $\geq 18$  year old) undergoing non-emergent coronary artery bypass grafting surgery (on and off pump) requiring a median sternotomy.

**Exclusion Criteria.**

- Concomitant cardiac procedures (e.g. aortic valve repair/replacement, mitral valve repair/replacement, aortic root replacements)
- Redo sternotomy.
- $< 50$  kg (Exparel® is currently only approved in patients  $> 50$  kg).
- Pregnant or nursing
- History of alcohol, narcotic or illicit drug abuse
- Participation in another study evaluating investigational medications within the past 30 days
- Taking narcotic analgesics within 3 days pre-operatively or perioperative stress-dose steroids.
- Chronic non-cardiac pain (e.g. lower back pain, fibromyalgia) requiring narcotic analgesics.
- Pre-operative mild liver insufficiency as defined by LFTs (i.e. ALT, AST)  $\geq 1.5$  times the upper limit of normal (ULN: ALT: 0-35 U/L, AST: 0-35 U/L, Alk Phos 35-105 U/L, Total bilirubin: 0-1.2 mg/dL)
- Pre-operative mild renal insufficiency (Cr  $\geq 1.5$  mg/dL)
- Allergy to amide-type anesthetics
- Recurrent ventricular arrhythmias, low cardiac output requiring inotrope and/or intra-aortic balloon pump support, LVEF  $< 30\%$  at time of pre-operative screening/evaluation.
- Unable to provide informed consent or unable to understand how to use pain rating scales.
- Inability to understand or operate the patient-controlled analgesia (PCA) machine.

**Withdrawal Criteria.**

Patients meeting these intra-operative and post-operative criteria will be withdrawn from the study because of the likelihood that these characteristics will independently affect primary and secondary study outcomes. However, primary and secondary outcomes will still be collected for these patients and results included in an “intention-to-treat” analysis.

- Post-operative intubation longer than 16 hours.
- Cardiopulmonary bypass time  $> 3$  hours or aortic cross-clamp time  $> 120$  minutes.
- Return to OR during hospital admission.

**Vulnerable Subjects.**

No vulnerable subjects will be included in this study. Only patients deemed competent to voluntarily consent to participation in this study will be included.

**III. METHODS AND PROCEDURES****Methods and Procedures.**

Refer to Appendix I for overview of Study Schedule.

### Patient enrollment

Screening procedures will be performed in the outpatient clinic, inpatient floor or cardiac cath lab. During the screening visit, medical/surgical history, vital sign measurements, and routine clinical laboratory tests, which are normally obtained in all cardiac surgery patients (complete metabolic panel, CBC, INR/PTT). If the patient meets eligibility criteria and is willing to participate, then informed consent will be obtained. Consenting patients will also undergo drug/alcohol screening and forced vital capacity (FVC) measurement prior to surgery. The patients will be trained on the pain assessment tools used during the study, including the adult NVPS and NRS (see Appendix II).

Prior to the planned operation, patients will be administered the Brief Pain Inventory to establish baseline pain scores (see Appendix III). The patient will also receive a sheet reviewing the NVPS and NRS pain assessment scales and be asked to rate their pain on the NRS scale. They will also be instructed on how to use the PCA pump prior to surgery.

On the day of surgery, the subjects' history, physical and labs will be reviewed by research staff to confirm study eligibility. They will also be instructed on how to use the incentive spirometer and their peak inspiratory capacity (IC) will be measured.

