**Figure 3.** Cross-sectional diagram of DepoFoam® drug delivery system containing aqueous chambers filled with Bupivacaine.

Reproduced from Chahar P, Cummings KC. *Liposomal bupivacaine: a review of a new bupivacaine formulation.* J Pain Research. 2012.

To compare differences in pain control, we will use a number of validated pain assessment tools. These include the adult nonverbal pain scale (NVPS), numerical rating scale (NRS) and brief pain inventory (BPI) (see Appendix II and III). The NVPS has been adopted by the cardiovascular ICU (CVICU) for assessing pain in critically-ill, intubated patients. It includes assessments of the patient’s face, body movements, muscle tension and vital signs to determine a total score ranging from 0 to 10. It has been shown to exhibit high reliability and inter-rater agreement, as well as increase patient and staff satisfaction. The NRS is an 11-point scale ranging from 0, “no pain”, to 10, “the worst possible pain”, that is used by nursing staff for

assessing and documenting pain in extubated, alert patients. The scale has shown high sensitivity and simplicity. Moreover it is interval and allows for parametric analysis. The BPI consists of four questions rating pain severity and seven questions regarding impact of pain on daily function, allowing calculation of pain severity and interference indices for comparison. Studies have shown that BPI scores correlate with the number of days from surgery and decreasing analgesic requirements.

Exparel® is not currently FDA-approved for peripheral nerve blocks. There are two ongoing clinical trials studying the use of Exparel® for femoral nerve blocks. However, Exparel® has not previously been studied for our specific application. Thus, we are conducting this study to evaluate the efficacy and safety of Exparel® in parasternal nerve blocks in cardiac surgery patients. Successful use of Exparel® for parasternal intercostal nerve blocks may revolutionize the management of post-cardiac surgery pain. Optimal pain control and reduced opioid doses would enable earlier extubation and mobilization, less opioid-associated morbidity and shorter ICU and total hospital lengths of stay.

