### Follow-up

The subjects will be seen by their primary care physician within 7-10 days per standard URMC protocol. They will return to clinic for a post-operative visit approximately 30 days from discharge. During this visit, they will be administered a brief questionnaire regarding presence/quality of continued pain following discharge (BPI-SF, see Appendix III). They will also be asked to rate the quality of their pain control during their hospitalization and recall their time to return to work or daily activities. During this visit, they will also be debriefed about the study.

In addition, in order to assess the success of maintenance of the blind, we will ask the subjects to: (1) guess which treatment (Exparel® or placebo) they think they received in the study, (2) express their degree of certainty regarding their guess, and (3) explain their reasons for their guess.

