### **Data Analysis.**

#### Data Analysis

- Patient demographics/Pre-op characteristics:
  - Age, sex, race, Body surface area (BSA)/BMI
  - Co-morbid diseases: Diabetes mellitus, COPD, smoking, hypertension, coronary artery disease
  - Left ventricular ejection fraction (%)

- Creatinine (Cr), Cr clearance
- Functional status: New York Heart Association (NYHA) class, American Society of Anesthesiologists (ASA) classification
- Intra-operative characteristics:
  - Operation type: CABG (on/off bypass), AVR, MV repair/replacement, Maze, Other (i.e. TV repair/replacement, ASD closure)
  - Internal mammary artery (IMA) harvested (one or two)
  - Cardiopulmonary bypass time (min)
  - Aortic cross-clamp time (min)
  - Intraoperative fentanyl ( $\mu\text{g}$ ), intraoperative versed (mg)
- Pain assessment:
  - Calculate mean area under the curve (AUC) for adult NVPS scores over the time intervals “0-2”, “0-4”, “0-8” and “0-12” hours.
  - Calculate mean AUC for NRS scores over the time intervals “0-12”, “0-24”, “0-36”, “0-48”, “0-60” and “0-72” hours.
- Opioid requirement:
  - Calculate mean cumulative fentanyl equivalent use for time intervals “0-2”, “0-4”, “0-8”, “0-12”, “0-24”, “0-36”, “0-48”, “0-60” and “0-72” hours.
  - Use of breakthrough pain medication (e.g. Toradol or Tramadol)
- ICU length of stay:
  - Calculate mean lengths of stay (hours) for placebo and Exparel® groups.
- Hospital length of stay:
  - Calculate mean lengths of stay (days) for placebo and Exparel® groups.
- Time to extubation:
  - Calculate mean time to extubation (hours) for placebo and Exparel® groups.
- Time to return of bowel function:
  - Calculate mean time to return of bowel function for placebo and Exparel® groups.
- Splinting
  - Mean change in IC from pre-operative to POD #1-2 in both treatment arms.
- Assessment of blind
  - Calculate the percentage of correctly guessed treatment assignments.

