### Statistical analysis

Descriptive statistics will be reported for each group. Means with standard deviation and 95% confidence intervals of the means will be reported for continuous variables and frequency and proportion distribution will be reported for categorical outcomes.

Student t-test (for normally distributed continuous variables) and Wilcoxon rank sum tests (for non-normally distributed variables) will be used to compare continuous outcomes such as AUC for adult NVPS/ NRS and opioid requirements between the two groups. For categorical outcomes, chi-square tests will be used to compare differences between the two groups. If some cell counts are small and the asymptotic tests are not reliable, then exact methods will be used. A general linear regression model for NRS scores will be applied to show the main effect for the treatment group, adjusting for covariates. Regression analysis will also be applied to opioid requirements. For the binary outcome of whether a patient has reached his/her maximum allowed dose of opioid, logistic regression models will be applied. For the opioid requirement outcome, patients who have reached their maximum allowed dose of opioid will be treated as censored and a Tobit regression model will be applied. Since there are two primary outcomes, a type I error of 2.5% will be used. All the tests will be two-sided.

Survival analyses will be applied for time to event data, such as the lengths of stay and mean time to return of bowel function. Logrank tests will be applied for simple comparisons between the two groups. Cox proportional hazards models will be used to facilitate the inclusion of covariates in the regression analysis. Note that although no censoring of subjects are expected in the study (i.e. the lengths of stay and mean time to return of bowel function will be observed for each patient) and a general linear regression analysis may be applicable, our survival analysis approach enables us to estimate the survival curves and read the different rates at different time points from the curves.

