**Appendix III: Brief Pain Inventory (Short Form)**

1. Throughout our lives, most of us have had pain from time to time (such as minor headaches, sprains, and toothaches). Have you had pain other than these everyday kinds of pain during the last week?

Yes

No

2. On the diagram, shade in the areas where you feel pain. Put an X on the area that hurts the most.

3. Please rate your pain by circling the one number that best describes your pain at its *worst* in the last week.

0	1	2	3	4	5	6	7	8	9	10
No										Pain as bad as
Pain										you can imagine

4. Please rate your pain by circling the one number that best describes your pain at its *least* in the last week.

0	1	2	3	4	5	6	7	8	9	10
No										Pain as bad as
Pain										you can imagine

5. Please rate your pain by circling the one number that best describes your pain on the *average*.

0	1	2	3	4	5	6	7	8	9	10
No										Pain as bad as
Pain										you can imagine

6. Please rate your pain by circling the one number that tells how much pain you have *right now*.

0	1	2	3	4	5	6	7	8	9	10
No										Pain as bad as
Pain										you can imagine

7. What treatments or medications are you receiving for your pain?

8. In the last week, how much relief have pain treatments or medications provided? Please circle the one percentage that most shows how much *relief* you have received.

0%	10%	20%	30%	40%	50%	60%	70%	80%	90%	100%
No Relief										Complete Relief

9. Circle the one number that describes how much, during the past week, pain has interfered with your:

A. General Activity

0	1	2	3	4	5	6	7	8	9	10
Does not Interfere										Completely Interferes

B. Mood

0	1	2	3	4	5	6	7	8	9	10
Does not Interfere										Completely Interferes

C. Walking Ability

0	1	2	3	4	5	6	7	8	9	10
Does not Interfere										Completely Interferes

D. Normal Work (includes both work outside the home and housework)

0	1	2	3	4	5	6	7	8	9	10
Does not Interfere										Completely Interferes

E. Relations with other people

0	1	2	3	4	5	6	7	8	9	10
Does not Interfere										Completely Interferes

F. Sleep

0	1	2	3	4	5	6	7	8	9	10
Does not Interfere										Completely Interferes

G. Enjoyment of life

0	1	2	3	4	5	6	7	8	9	10
Does not Interfere										Completely Interferes

Scoring:

Pain Severity Score = Mean of items 3–6 (pain at its worst, pain at its least, average Pain Interference Score = Mean of items 9A–9G (interference of pain with: general activity, mood, walking, normal work, relations, sleep, enjoyment of life)

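### The Brief Pain Inventory is collected before surgery and at follow-up, but no stated analysis names it; comparing the follow-up indices with adjustment for baseline would use data already in hand

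*Combined protocol and SAP*

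**What the plan says.** The Background presents the BPI as one of three tools for comparing pain control between arms, "allowing calculation of pain severity and interference indices for comparison". Under Patient enrollment, before the operation, "patients will be administered the Brief Pain Inventory to establish baseline pain scores". The Follow-up section repeats the short form at the clinic visit about 30 days after discharge. Appendix III gives the scoring: "Pain Severity Score = Mean of items 3–6", and interference as the mean of items 9A to 9G.

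The Data Analysis list covers two pain instruments, the NVPS and the NRS (for the latter, "Calculate mean AUC for NRS scores over the time intervals" up to 72 hours). It has no BPI entry. In the Statistical analysis section:

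- t-tests or Wilcoxon tests "will be used to compare continuous outcomes such as AUC for adult NVPS/ NRS and opioid requirements between the two groups".
- Covariate adjustment is written for other outcomes: "A general linear regression model for NRS scores will be applied to show the main effect for the treatment group, adjusting for covariates", with regression also for opioid requirements, logistic regression for reaching the maximum opioid dose, and Cox models for time-to-event outcomes.
- The longitudinal models are for variables, such as NRS, measured repeatedly over the 72-hour period.

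The BPI is not mentioned in any of these.

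**The concern.** A measure is taken twice, its baseline role is stated and its scoring is defined, but the plan does not say how the arms will be compared on it. If the general rule is applied by default, the follow-up indices are compared without the baseline, and differences between patients in pre-existing pain stay in the error term. Such differences are possible. The questionnaire asks about pain in general over the last week, and the exclusion for chronic non-cardiac pain applies only where narcotics are required.

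At stake is precision on the only validated measure of pain and function scheduled after discharge. With no stated analysis, the choice between raw scores, change scores and adjusted scores is also open once the data are seen.

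**Working it through.** **1. Where the BPI could enter the analysis.** The longitudinal models do not fit a pair of values taken before surgery and at follow-up. The adjusted regressions are each tied to a different outcome. That leaves the two-sample rule for continuous outcomes, which is introduced by examples and so could cover the BPI. It has no baseline term.

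**2. The plan's own power figures.** Inputs from Number of subjects: 39 per arm, two-sided 2.5%, a 30% decrease, SD falling in proportion.

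- NRS: difference 0.3 × 53.2 = 15.96; SDs 24.1 and 0.7 × 24.1 = 16.87; SE = √[(24.1² + 16.87²)/39] = 4.71; ratio 3.39. Noncentral-t power is 86.2%, against 86% stated.
- Opioid use: difference 0.3 × 23.2 = 6.96; SDs 8.3 and 5.81; SE = 1.62; ratio 4.29. Power is 97.6% by noncentral t and 98.0% by the normal approximation, against 98% stated.

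Both reproduce, and neither involves the BPI.

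**3. Effect of adjusting the follow-up BPI for baseline.** The documents give no BPI SD, target difference or correlation, so results are in SD units over an assumed range of r. Two-sided 5% is also an assumption.

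- Unadjusted: SE = √(2/39) = 0.2265 SD. The difference with 80% power is 0.643 SD (noncentral t, 76 df).
- Adjusted: variance ratio f = (1 − r²) × [1 + 1/(2n − 4)]. With n = 39 this is (1 − r²) × (1 + 1/74) = (1 − r²) × 1.0135. The second factor is the cost of estimating the baseline slope. Equivalent size per arm is 39/f. Power uses 75 df and noncentrality 0.643/(0.2265√f).

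| r (assumed) | Variance ratio f | Equivalent n per arm | Power at 0.643 SD |
|---|---|---|---|
| 0 | 1.014 | 38.5 | 79.5% |
| 0.2 | 0.973 | 40.1 | 81% |
| 0.3 | 0.922 | 42.3 | 83.1% |
| 0.5 | 0.760 | 51.3 | 89.5% |
| 0.6 | 0.649 | 60.1 | 93.5% |

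Break-even is where (1 − r²) × (75/74) = 1, so r² = 1/75 and r is about 0.12. With 37 per arm (39 × 0.95 = 37.05, the plan's 5% dropout) the ratios barely change: 1.014 at r = 0 and 0.649 at r = 0.6.

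**4. Why not a change score.** With equal variances at the two times, its variance relative to the raw follow-up score is 2(1 − r): 1.4 at r = 0.3, 1.0 at r = 0.5 and 0.8 at r = 0.6. It is worse than ignoring baseline whenever r is below 0.5.

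**5. Chance imbalance at baseline.** Its standard deviation is √(2/39) = 0.23 SD, which moves the unadjusted estimate by 0.5 × 0.23 = 0.11 SD at r = 0.5. This is not a further loss. The unadjusted variance 2/39 splits into r² × 2/39 from baseline imbalance and (1 − r²) × 2/39 from the rest, so the usual standard error already carries it.

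**The case against.** A reader might infer that the plan compares the follow-up BPI unadjusted. The documents do not say so: no BPI analysis is stated, and the two-sample test reaches it only as a general rule. A reader might also infer that the baseline BPI enters no analysis at all. That cannot be shown. The covariates for the NRS and opioid regressions are not listed, and the Data Storage section records a baseline pain assessment score without naming the instrument, so baseline BPI could be a covariate there. Neither point supplies a baseline-adjusted analysis of the follow-up BPI itself.

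The stronger objection is that r may be low. Baseline is pain before a sternotomy, and recent surgical pain may dominate at follow-up. Excluding narcotic-requiring chronic pain and recent narcotic use may also narrow the baseline spread. At r of 0.2 or less the gain is nil or under 3% of variance. This stands, and it is why the range must start at 0. Even there the loss is about half a percentage point of power.

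It is also fair that the indices are bounded at 0 and may be skewed, and that the existing rule provides a Wilcoxon test for that case. A linear model should not remove that protection without a substitute.

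Finally, the BPI is not among the primary outcomes or the listed secondary ones, so little in the trial's main conclusions depends on it. That limits the weight of the point.

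**Conclusion.** The point holds as a low-cost improvement. No stated analysis names the BPI at baseline or follow-up, and the only rule that would reach the follow-up indices ignores the baseline collected for them. Adjusting for the matching baseline index changes the variance by a factor of 1.01 (r = 0) to 0.65 (r = 0.6). Power at 0.64 SD moves from 80% to between 79.5% and 93.5%. These figures assume 39 per arm, a two-sided 5% test, a linear baseline relation and a correlation that the documents do not supply.

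The gain is efficiency alone. It would be wrong to read the unadjusted comparison as biased or as having an inflated error rate, because randomisation keeps its type I error nominal. The primary analyses and their stated power are untouched.

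**What to change.** Add the BPI severity and interference indices to the Data Analysis list, and add to the Statistical analysis section:

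- Each index at follow-up will be compared between arms by a linear model with arm and the same index at baseline. The adjusted difference with its confidence interval is the reported result.
- If residuals are clearly non-normal, a rank-based analysis of covariance or a Wilcoxon test will be given as a sensitivity analysis.

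This replaces the general two-sample test as the main analysis of the BPI only. It needs no new data, visits or patients. It uses one degree of freedom, and the worst case in the range examined is a variance increase of about 1.4%, when baseline carries no information. Stating it now also settles the choice among raw, change and adjusted scores before unblinding.

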### Randomization and Blinding

Patients will be randomized on the day of surgery to either placebo or treatment group. The subjects will be randomized in blocks of 4 to ensure a 1:1 ratio of placebo to treatment groups.

- Placebo: 0.9% normal saline
- Treatment group: 0.53% Exparel®

A randomization sheet will be generated by the study pharmacist, listing the randomization schedule in sequence for each block. The study pharmacist will have control of the randomization sheet. At the time of randomization, he will go to the next available row to determine which medication to dispense. The randomization sheet will document each subject's number, initials, date of surgery and study arm (active or placebo).

The study pharmacist will hold the key identifying which study group corresponds with which letter. In order to maintain blinding of the study investigators, the pharmacist will not reveal the subject's group assignment and data collection will be done according to the subject number. At quarterly intervals during the trial, the study pharmacist will reveal the blinding to the Independent Data/Safety Monitor (DSM) only. This will enable the Independent DSM to capture for any alarming trends in adverse events or serious adverse events as they are occurring. At completion of data collection and analysis for the entire study, the pharmacist will provide the study investigators with a copy of the report revealing which subject belonged to which study group.

The subjects will be blinded to their study arm and remain blinded for the entire duration of this study. Subjects who wish to know which drug they received (Exparel® or placebo), may contact the PI or co-PI and they will be informed of their study group following completion the study.

The study investigators, surgeon administering the medications, operating room staff and ICU/floor staff will all remain blinded. Only the pharmacist who will prepare and dispense the medication will be unblinded.

### Anesthetic Regimen

A standard anesthetic regimen to promote early extubation will be used, per our institutions protocols. The regimen will include:

- Pre-induction with midazolam.
- Induction with midazolam, fentanyl/sufentanyl, vecuronium/rocuronium, and isoflurane.
- Maintenance of intra-operative anesthesia with isoflurane and vecuronium/rocuronium.

Intraoperative monitoring will include standard ASA monitor, an arterial catheter and a central venous catheter. Pulmonary arterial catheters and transesophageal echocardiography will be used per institutional standards.

